4.5. Subgroup Analysis

Pre-specified subgroups were developed a priori for scientific interest and exploratory analyses. Multivariate and subgroup analyses are considered supportive without control of alpha and the additional endpoint analyses are likewise supportive without control of alpha.

The following pre-specified subgroups will be evaluated:

- Age (< 80 vs ≥ 80)
- Sex
- Admission NIHSS (median split)
- TLSW between 6 and ≤ 12 hours vs >12 to 24 hours
- Clinical imaging mismatch (CIM) category
- Wake-Up, Witnessed, and Unwitnessed
- Baseline occlusion location (ICA vs. M1)

4.6. Sample Size Estimate and Justification

The adaptive sample size was judged through simulations based on the following assumptions:

STRYKER CONFIDENTIAL - THIS DOCUMENT CONTAINS CONFIDENTIAL AND PROPRIETARY INFORMATION THAT IS THE PROPERTY OF STRYKER CORPORATION. NEITHER THIS DOCUMENT NOR THE INFORMATION HEREIN MAY BE REPRODUCED, USED, OR DISCLOSED TO ANY THIRD PARTY WITHOUT THE PRIOR WRITTEN CONSENT OF STRYKER CORPORATION

Stryker Neurovascular

Document Title: DAWN™ Trial Statistical Analysis Plan

Document Number: CDM10000704

Rev: AB

We investigated treatment effects that increased the expected weight in the active arm by 0, 0.5, 0.75, 1.0, 1.25, and 1.5 units above control for all infarct sizes. The effect size of 0.5 units of weight is small, and consequently this trial is not powered (30%) for this size. The effect sizes of 1.25 and 1.5, on the other hand, are very large and the trial offers better than 95% power to detect such improvements. The design provides 86% power to detect an effect size of 1 unit. The Type I error probability is controlled to be no more than 2.5%.

Expected sample sizes are smallest when the treatment effect is very small (when early stopping for futility is likely) and when the treatment effect is very large (when early stopping for expected success is likely). The trial enrolls more subjects when the data are inconclusive about whether the device has a significant positive effect.

The distribution of mRS outcomes for the control arm in the simulations was based on combined data from the following study sub-populations: IMS III IV tPA arm (N=222); MR RESCUE penumbral pattern with IV tPA arm (N=34); PROACT II heparin arm (N=59); MELT no treatment arm (N=57); DEFUSE 2 Target Mismatch without reperfusion arm (N=32); Merci Registry non-revascularized, non-intubated, treated ≥ 6 hours (N=30) [Sponsor-derived from raw dataset]; Natural History of MCA and ICA occlusions (N=40); and SENTIS no treatment arm (N=106). The distribution of the mRS outcomes for the control arm used in the simulations is shown in **Table 1**.

TABLE 1. DISTRIBUTION OF MRS OUTCOMES FOR THE CONTROL ARM IN THE SIMULATIONS

mRS	0	1	2	3	4	5	6
Proportion	0.07	0.13	0.12	0.17	0.20	0.11	0.19

4.7. Control of Systematic Error/Bias

In order to control systematic error/bias, the randomization will be take place using either the use of an independent IVRS or web based system or through pre-printed, block randomization envelopes prepared by a qualified and independent biostatistician.

In order to protect the status of the blind and minimize potential bias, an independent statistician who is not involved with the conduct of the study will perform the interim analyses for the primary endpoint.

STRYKER CONFIDENTIAL - THIS DOCUMENT CONTAINS CONFIDENTIAL AND PROPRIETARY INFORMATION THAT IS THE PROPERTY OF STRYKER CORPORATION. NEITHER THIS DOCUMENT NOR THE INFORMATION HEREIN MAY BE REPRODUCED, USED, OR DISCLOSED TO ANY THIRD PARTY WITHOUT THE PRIOR WRITTEN CONSENT OF STRYKER CORPORATION

The design mitigates potential bias due to the enrichment by preventing early stopping for expected success immediately following an enrichment decision. We require an additional 100 subjects to be enrolled in the enriched population before making a decision to stop enrollment.

4.8. Eligibility of Subjects, Exclusions, and Missing Data

Based on previous experiences in clinical trials of acute stroke, minimal loss to follow-up (LTFU) is expected for the 90-day assessment of the primary outcome measure. In the MERCI study, 7.2% (11/151) of subjects were LTFU, in Multi MERCI 2.4% (4/164) were LTFU, and in the TREVO 2 study, 3.4% (6/178) were LTFU. All efforts should be made to ensure near complete follow-up, with particular focus on the assessment of the primary outcome (mRS at 90 days) and mortality.

Nevertheless, some missing data may still occur. All randomized subjects will be included in the primary endpoint analysis (ITT). In case of missing 90-day mRS values, the 30-day mRS values will be incorporated into a multiple imputation model. In case of missing 90-day and missing 30-day mRS values, multiple imputation models will incorporate the day 5-7mRS; if that also missing, the subject will be counted as a failure (mRS 6). For conventional statistical analysis of the 90 day mRS and descriptive statistics (e.g. distribution of of mRS) will use LOCF of 30 day data. Refer to the adaptive design plan for details in Appendix F of study protocol.

4.9. Population Definitions

Screened: Includes any subject who is considered for participation for the trial, whether or not they sign an informed consent.

Screen-failed: Includes any subject who is considered for participation for the trial, who either fail to meet one or more of the inclusion criteria or who meet one or more of the exclusion criteria; subjects can be screen failed based on general inclusion/exclusion criteria, or imaging inclusion/exclusion criteria (these subjects may or may not have signed an informed consent).

Enrolled: Includes any subject who has been randomized based upon the results of the RAPID post-processing of the baseline MRI-DWI or CTP-rCBF baseline images, and Clinical Imaging Mismatch profile (informed consent must be obtained prior to randomization).

Completed: Includes any subject who is enrolled/randomized and completes the study follow up at Day 90 (± 14), or is known to have expired before 90 days post randomization.

Discontinued: Includes any subject who is enrolled/randomized but who fails to complete the study follow up at Day 90 (± 14), and who has not expired before 90 days post randomization.

Wake-up Strokes: Subjects known to have symptoms first detected on awakening from sleep.

Witnessed Strokes: Subjects with last known well time and symptoms first observed time known to be the same.

Un-witnessed Strokes: Subjects with last known well time and symptoms first observed time known to be different, but not known to have symptoms first detected on awakening from sleep.

4.10. Analysis Populations

Intent-to-Treat (ITT): Includes all enrolled/randomized subjects. All randomized subjects will be included in the ITT analysis, where the arm classification is based on the randomized arm, even if they never receive it or receive treatment with another procedure. If the final analysis is only on the enriched population (refer to adaptive design plan in Appendix F of study protocol) then only those subjects in the enriched group will be included in the final analysis, based in ITT. This population is the primary population for all efficacy parameters.

As-Treated Analysis (AT): The same as the ITT population except subjects are analyzed based upon actual treatment received. Subjects who receive only medical therapy are included in the control arm, and subjects who receive any device-based therapy are included in the Trevo arm.

Per-Protocol (PP): A subset of the intent-to-treat population, including subjects who did not violate the inclusion/exclusion criteria or experience significant protocol deviations.

4.11. Estimated Duration of Subject Participation

Subjects will be followed for 90 (± 14) days post-procedure, with data collection 24(-6/+24) hours post randomization, on the day of hospital discharge or 5 to 7 days (whichever occurred sooner), 30 days (± 14 days), and 90 days (± 14 days) post-procedure. Subjects who do not withdraw prematurely from the study will be followed for a maximum of 104 days following the study procedure. Any subject who discontinues from the study for any reason will be followed to monitor safety for the duration of the study. If a subject withdraws from the study with an existing adverse event, regardless of the relationship to the study device or procedure, the subject will only be followed for a maximum of 104 days following their study procedure date.

Stryker Neurovascular

Document Title: DAWN™ Trial Statistical Analysis Plan

Document Number: CDM10000704

Rev: AB

TABLE 2. DAWN STUDY TIME AND CLINICAL ASSESSMENT SCHEDULE

Event	Screening/ Baseline	Procedure (Treatment Arm Only)	24 Hr (-6/+24) (post randomization)	Day 5-7 / Discharge (whichever is earlier)	Discharge	Day 30 ± 14	Day 90 ± 14
Inclusion/Exclusion Criteria	✓						
Demographics/Medical History/Baseline Medications	✓						
Baseline Characteristics	✓						
Baseline Labs	✓						
Informed Consent	✓						
Randomization (t=0)	✓						
Angiography Procedure Details (Treatment Arm only)		✓					
mRS [†]	✓ (pre stroke)			✓ [†]		✓ [†]	✓ [†]
NIHSS	✓ [*]		✓ ^{**}	✓		✓	✓
Neuro imaging (to assess for hemorrhage, occlusion location/vessel patency & infarct volume)***	✓ MR-DWI/MRA or CT/CTA/CTP		✓ MR-DWI/MRA or CT/CTA	✓ MR-DWI or CT (optional)			
AEs/SAEs (from time of randomization)		✓	✓	✓		✓	✓
Concomitant Medications		✓	✓	✓		✓	✓
In Hospital Med Management					✓		
Intubation Details					✓		
UB04					✓		

*NIHSS should be obtained within 1 hour of corresponding core infarct measurement.

** NIHSS should be obtained within 2 hours of the 24 (-6/+24) hour neuro-imaging to determine presence/absence of hemorrhage. [†] Must be conducted by an individual blinded to the treatment arm.

*** CT/MR and Angiographic images should be de-identified before being submitted to Stryker NV or core lab.

4.12. Analyses Schedule

STRYKER CONFIDENTIAL - THIS DOCUMENT CONTAINS CONFIDENTIAL AND PROPRIETARY INFORMATION THAT IS THE PROPERTY OF STRYKER CORPORATION. NEITHER THIS DOCUMENT NOR THE INFORMATION HEREIN MAY BE REPRODUCED, USED, OR DISCLOSED TO ANY THIRD PARTY WITHOUT THE PRIOR WRITTEN CONSENT OF STRYKER CORPORATION

Data analyses will occur according to the required timeframes for submission of study reports to the Food and Drug Administration (FDA). A final analysis will occur upon study completion.

4.13. Interim Analysis

Primary endpoint interim analyses will begin after 150 subjects have been enrolled, and subsequent interim analyses will take place after every 50 subjects.

The analysis performed at each interim analysis will include:

- Modeling of the treatment effect for each infarct size in the population,
- Longitudinal modeling to impute final outcomes for subjects for which we have 30-day mRS scores but not 90-day mRS scores, and
- Estimation of the distribution of infarct sizes.

The mathematical details and assumptions for these analyses are described in Appendix F.

The possible adaptations that may be made at the interims are to:

- Stop the trial for futility,
- Enrich the population if it appears that the device benefits one subset of the population considerably more than another, or
- Stop enrollment for expected success.

The rules for each decision/adaptation are defined below. Additional details pertaining to statistical models are given in the adaptive design plan in Appendix F of Study protocol.

4.13.1. *Interim Monitoring for Early Futility*

Interim safety analyses will be performed concurrently with the primary endpoint analyses.

The trial stops for futility if there is less than 10% predictive probability that the trial would be successful if enrolled to the maximum sample size under any enrichment possibility.

4.13.2. *Enrichment*

Enrichment decisions can occur starting at 150 subjects enrolled and the last opportunity to enrich is at 400 subjects. The candidate enriched populations that the trial considers are based on infarct sizes. The five possible subpopulations are defined by infarct size as measured using RAPID MR-DWI or CTP-rCBF maps:

1. The full population of infarct sizes 0 to 50 cc
2. Infarct sizes of 0 to 45 cc
3. Infarct sizes of 0 to 40 cc
4. Infarct sizes of 0 to 35 cc
5. Infarct sizes of 0 to 30 cc

If the population is enriched, subjects with larger infarct sizes are no longer enrolled, and the final efficacy analysis omits subjects with larger infarct sizes from consideration. Enrichment decisions are irreversible, but the trial can enrich the population further after it has already been enriched.

The design will enrich if one of the following conditions is met:

If the highest currently open group of five (5) cc infarct sizes has less than 40% posterior probability of an average positive treatment effect on mRS, then this group of infarct sizes will no longer be enrolled in the trial. This rule is applied before the second enrichment rule, and may only be applied once per interim analysis.

If the predictive probability of a positive trial increases by at least 10% by enriching to a smaller subpopulation, then the trial will enrich to the smallest subpopulation that satisfies this criterion.

4.13.3. Interim Monitoring for Expected Success

The trial may only stop enrollment for expected success if at least 100 subjects have been enrolled since the last enrichment or no enrichment has been made and at least 200 total subjects have been randomized. The decision is based on the predictive probability of trial success for both the weighted mRS analysis and dichotomous mRS analysis, and if no further subjects are enrolled. The threshold for this predictive probability is 95% for the 200 and 250 subject interim analyses, 90% for the 300 and 350 subject interim analyses, 85% for the 400 subject interim analysis, and 80% for the 450 and 500 subject analyses. If the predictive probability exceeds the threshold at an interim analysis, then enrollment stops for expected success. All subjects will be followed through their 90-day assessment and the final analysis for trial success will be based on the full data through 90 days.

In order that the trial stop for expected success, the predictive probability of trial success must exceed the threshold described above, and the analogous predictive probability of trial success for the dichotomized version of the utility function must also exceed the same threshold. The dichotomized utility function is also discussed in Appendix F.

4.13.4. Longitudinal Model

At the time of each interim analysis, some subjects may not have completed the 90-day follow-up period for mRS. Because subjects will also be evaluated for mRS at 30 days these scores will be used to assist in making decisions at the interims. We estimate the probability distribution of 90-day mRS conditional on 30-day mRS and use this estimated distribution to inform a longitudinal model for multiply imputing final mRS outcomes for subjects with known 30-day mRS but unknown 90-day mRS.

4.14. Efficacy Analyses

The final analysis will be performed only on the enriched population if an enrichment occurs, and assumes a constant treatment effect over all infarct sizes that are in the population at the end of the trial.

The trial is considered successful if there is sufficiently high posterior probability that the treatment effect is positive. The threshold for success is adjusted (increased) to account for any enrichment that occurred to and depends on the following factors:

- The number of enrolled subjects in the enriched population at the time of the enrichment decision (N_1)
- The number of enrolled subjects outside the enriched population (N_2)
- The number of subjects enrolled after the enrichment decision (N_3).

Specifically, the threshold is calculated as:

$$\Phi\left(\sqrt{1 + \frac{N_2}{N_1 + N_3}} \Phi^{-1}(p_{crit})\right),$$

where Φ is the standard normal cumulative distribution and $p_{crit} = 0.986$ is a critical probability evaluated via simulation to control Type I error probability. If no enrichments are made during the trial, then the success threshold is equal to p_{crit} , and the threshold increases as enrichment becomes earlier and more aggressive.

The primary analysis of mRS scores for the interim and final analyses will be performed by Berry Consultants, LLC using custom code developed in Java and R software.

The Secondary efficacy and safety analyses will be performed by Stryker NV Biostatistics team using SAS, version 9.4 or higher.

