Statistical Test Method	The alternative hypothesis is that the proportion of subjects functionally independent (mRS 0-2) and the average of the weighted mRS categories at 90 days in the Trevo Thrombectomy plus Medical Management group is superior to Medical Management alone. The final analysis is a Bayesian analysis of the 90-day mRS scores, and declares success if there is sufficiently large posterior probability that the overall treatment effect is positive. The threshold for success if no enrichments are made is 0.986, and this threshold increases as the enrichment becomes earlier and more aggressive. The adjusted thresholds are to control type I error. Enrichment decisions and early stopping rules are based on Bayesian predictive probabilities outlined in the Adaptive Design Plan in Appendix F .

Document Number: CDM10000146

Rev: AD

Sample Size Parameters	The sample size for the trial is assessed through simulation, which considered effect sizes ranging from zero to a 1.5 increase on the weighted mRS scale. For one-sided Type I error probability of 2.5%, the design has 86% power for a 1 unit increase in weighted mRS.

Document Number: CDM10000146

Rev: AD

1	Intro	duction and Rationale	13		
	1.1	Incidence and Burden of Stroke	13		
	1.2	Current Treatment Options	13		
	1.3	Unmet Need in Acute Ischemic Stroke	13		
	1.4	Purpose of Study	15		
2	Study	7 Device	15		
	2.1	Study Device Description	15		
	2.2	Study Device Labeling	17		
3	Study	Study Objective			
	3.1	Primary Objective	18		
	3.2	Secondary Objectives	18		
4	Study	7 Endpoints and Safety Outcomes	18		
	4.1	Primary Endpoint	18		
	4.2	Secondary Endpoints	19		
	4.3	Primary Safety Outcome	19		
	4.4	Secondary Safety Outcomes	19		
5	Study	Study Design			
	5.1	Overview	20		
	5.2	Justification for the Study Design	22		
		5.2.1Justification for Expansion of Time Window			
		5.2.2Justification for Inclusion of Wake up and Unclear Onset Strokes			
		5.2.3Justification for Inclusion of IV tPA Failures			
		5.2.4Justification for Non Reliance on Penumbra Imaging			
		5.2.5Justification for Use of Clinical Imaging Mismatch Criteria			
		5.2.6Justification for Use of Standardized Core Infarct Imaging Software			
		5.2.7Justification for Use of Weighted mRS as Primary Endpoint			
		5.2.8Justification for Use of Adaptive Design			
	5.3	Method of Assigning Subjects to Treatments			
	5.4	Blinding and Breaking the Blind	33		
6	Study	Study Population			
	6.1	- Inclusion Criteria	34		

Document Number: CDM10000146

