4. STATISTICAL METHODS

4.1. Primary Statistical Null Hypothesis

There are hierarchically nested co-primary analyses of the 90-day mRS values between the two arms. For the analysis of the weighted mRS values at 90-days the null hypothesis is that the mean weighted mRS value is equal in the two treatment groups. The alternative hypothesis to be tested is that the mean utility is greater in the Trevo Thrombectomy plus Medical Management (Active) treatment arm than the Medical Management alone (Control). For the analysis of the proportion of subjects functionally independent (mRS 0-2) at 90 days in the null hypothesis is that the probability of a functionally independent subject in each treatment group are equal, with an alternative that the probability of a functionally independent subject on the Active arm is larger than for the control arm.

For each co-primary hypothesis test the analysis is based on a Bayesian analysis. Success will be considered for the weighted mRS co-primary analysis first, and will be declared if the posterior probability of the alternative hypothesis (superiority) is sufficiently large. Only if the weighted mRS co-primary analysis is positive will analysis then proceed to the nested dichotomous analysis. For the nested analysis, success will be declared if the posterior probability of the alternative hypothesis (superiority) is sufficiently large. The threshold for success if no adaptive enrichments are made is 0.986, and this threshold increases if adaptive enrichments occur. The adjusted thresholds are to control type I error and are detailed in the Adaptive Design Plan in Appendix F of Study Protocol.

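### Does the success threshold really rise with earlier enrichment, as the plan says, and does the wording matter?

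*SAP*

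**What the plan says.** SAP 4.14 and Protocol 8.7 print the same success threshold:

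Φ( √(1 + N2/(N1+N3)) × Φ⁻¹(p_crit) ), with p_crit = 0.986.

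N1 is "The number of enrolled subjects in the enriched population at the time of the enrichment decision". N2 is "The number of enrolled subjects outside the enriched population". N3 counts those enrolled after that decision. Both sections say that p_crit was set by simulation to control type I error and that the threshold equals p_crit if there is no enrichment. They then add "and the threshold increases as enrichment becomes earlier and more aggressive". The Protocol synopsis, under Statistical Test Method, has "this threshold increases as the enrichment becomes earlier and more aggressive".

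SAP 4.1 describes the same rule without mentioning timing. It says "The threshold for success if no adaptive enrichments are made is 0.986" and "this threshold increases if adaptive enrichments occur", and refers to the Adaptive Design Plan for detail.

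On timing, SAP 4.13.2 says "Enrichment decisions can occur starting at 150 subjects enrolled and the last opportunity to enrich is at 400 subjects". SAP 4.13.3 allows enrollment to stop for expected success after an enrichment only if "at least 100 subjects have been enrolled since the last enrichment".

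**The concern.** The adjusted threshold is the plan's stated protection against type I error when the population is narrowed on interim data. A reader of the sentence would expect the earliest enrichment to face the strictest bar. Put the same cut-off at different looks into the formula, with the final size held constant, and the earliest enrichment gets the lowest bar of the enriched options.

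A mismatch between a formula and its description raises the question of which one was simulated when 0.986 was chosen. If the simulations had used some other rule, one that does become stricter for early enrichment, the printed formula would not be the calibrated one and the stated 2.5% error rate would not be assured.

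**Working it through.** **Inputs.** p_crit = 0.986, so Φ⁻¹(p_crit) = 2.1973 (SAP 4.14). Enrichment may occur at n = 150 to 400 enrolled (SAP 4.13.2). The maximum enrollment is N = 500 (SAP 3). The share f of enrolled subjects outside the retained infarct range is not given, so it is assumed to lie between 5% and 30%. A single enrichment is assumed.

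**The plan's own figure.** With N2 = 0 the square root is 1 and the formula returns 0.986, as stated.

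**What the formula depends on.** Since 1 + N2/(N1+N3) = (N1+N2+N3)/(N1+N3), the critical z-value is multiplied by the square root of all enrolled over those retained. Timing enters only through that ratio.

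**Fixed share, fixed final size.** Put N2 = f·n, N1 = (1−f)·n and N3 = N − n. The ratio N2/(N1+N3) is f·n/(N − f·n), and its derivative in n is f·N/(N − f·n)², which is positive. Later enrichment therefore gives the higher threshold. With N = 500:

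| f | n = 150: ratio | threshold | n = 400: ratio | threshold | one-sided tail, 150 vs 400 |
|---|---|---|---|---|---|
| 5% | 7.5/492.5 | 0.9866 | 20/480 | 0.9875 | 1.34% vs 1.25% |
| 10% | 15/485 | 0.9872 | 40/460 | 0.9890 | 1.28% vs 1.10% |
| 20% | 30/470 | 0.9883 | 80/420 | 0.9917 | 1.17% vs 0.83% |
| 30% | 45/455 | 0.9894 | 120/380 | 0.9941 | 1.06% vs 0.59% |

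Without enrichment the tail is 1.40%, so every row is stricter than the unenriched rule.

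**Fixed share, 100 enrolled after enrichment.** The ratio is f·n/((1−f)·n + 100), which also rises with n. At n = 150 and n = 400 the thresholds are 0.9883 and 0.9890 (f = 10%), 0.9904 and 0.9917 (f = 20%), and 0.9924 and 0.9941 (f = 30%).

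**Fixed excluded count, fixed final size.** With N2 = 60 and N = 500 the ratio is 60/440 at every look and the threshold is 0.9904 throughout. Timing has no effect.

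**Comparisons in which earlier is stricter.**
- With N2 = 60 and the trial ending 100 subjects after enrichment, the ratio is 60/190 at n = 150 (0.9941) and 60/440 at n = 400 (0.9904).
- With f = 20%, enriching at 150 and stopping at 250 gives 30/220 (0.9904). Enriching at 250 and running to 500 gives 50/450 (0.9897).

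In both cases the final size differs between the trials compared; in the first, the excluded share differs too.

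**More aggressive enrichment.** At n = 250 and N = 500, f = 10%, 20% and 30% give 0.9879, 0.9897 and 0.9914. That half of the sentence is right.

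**The case for a change.** The best argument for a change is that the clause describes the pre-specified success criterion, stands in three places, and states a direction without conditions. With the share fixed, the direction is the opposite whether the final total or the number enrolled after enrichment is held constant. SAP 4.1 already has wording that is correct, so the correction would cost almost nothing. Appendix F, which holds the simulation detail, is not in the text available for this review, so the simulated rule cannot be confirmed from it.

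The algebra stands. The clause is not true in general, and under the most natural comparison it is backwards.

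The inference to a miscalibrated threshold does not stand. Neither document hints at a second rule. Both introduce the formula as the specific calculation and tie 0.986 to simulation directly beneath it. The clause has no functional form, so nobody could have programmed a threshold from it. Nor is the direction reversed in every realised trial: final size and excluded share both vary in this design, and some permitted paths give the earlier enrichment the higher bar.

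**Conclusion.** The word about timing is a slip in a descriptive clause, and no change to the plan is needed. An analyst following either document computes the threshold from the same formula and reaches the same conclusion whether or not the clause is reworded. The purpose of the adjustment, a bar above 0.986 whenever subjects have been excluded, is met in every case examined.

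With 500 enrolled, the difference between the first and last permitted looks is about 0.001 in the threshold at an assumed 5% excluded share and about 0.005 at 30%. Those sizes rest on the assumed share and on a single enrichment. For a fixed share and fixed final size, the direction holds for any share between 0 and 1. None of this is evidence of type I error inflation. That conclusion takes the printed formula to be the one simulated, which is how both documents present it.
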